### Medicines whose exposures may be affected by azd9291 that AstraZeneca considers may be allowed with caution

AZD9291 may increase the concentration of sensitive BCRP substrates (concentration of the sensitive BCRP substrate, rosuvastatin, is increased).

**Table 7 Exposure, pharmacological action and toxicity may be increased by AZD9291**

Warning of possible interaction	Advice
Rosuvastatin	Drugs are permitted but caution should be exercised and patients monitored closely for possible drug interactions. Please refer to full prescribing information for all drugs prior to co-administration with AZD9291.
Sulfasalazine	
Doxorubicin	
Daunorubicin	
Topotecan	

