### **4.1 Study Plan**

This study has been subject to an internal review according to AstraZeneca standard procedures.

Concomitant treatments, other than anti-cancer treatments, should be taken according to local medical practice. There are no restrictions on concomitant use in this study except per exclusion criteria. However, it is advised that those medical products and other products known to have interactions with AZD9291 should be avoided (see [Appendix B](#)).

The latest version of the IB and any subsequent updates will be supplied to the investigator. Investigators need to become familiar with the content of the IB and appendices associated with this protocol.

[Table 4](#) below outlines data collection measures that are considered for this study:

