### **4.3 Discontinuation from study treatment**

Patients may be discontinued from AZD9291 treatment in the following situations:

- The investigator thinks that it is in the patient's best interest to stop therapy (i.e. disease progression or patient is no longer receiving clinical benefit)
- Patient decision: the patient is at any time free to discontinue treatment, without prejudice to further treatment.
- Confirmed diagnosis of ILD
- Ulcerative ocular events
- QTc interval prolongation with signs/symptoms of serious arrhythmia
- Other manifestation of unacceptable toxicity
- Pregnancy
- Patient incorrectly enrolled or treated on the study
- Patient starts receiving additional anti-cancer therapy

- Lost to follow up (unsuccessful contact with patient despite every effort made by investigator)
- Termination of the study (see Sections 4.4 and 10.2.4)

All unused investigational product (IP) must be returned by the patient or representative (e.g. caregiver, family member).

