### 2.2 Violations and deviations

All major deviations related to the study inclusion or exclusion criteria and study conduct will be listed and summarised.

The following general categories will be considered major deviations. This list is not exhaustive and additional important deviations may be added prior to database lock.

- Informed consent procedure deviation Missing subject' signature from the informed consent document or other International Conference on Harmonisation - Good Clinical Practice (ICH-GCP) violation related to informed consent; laboratory or urinalysis samples or electrocardiogram (ECG) date before informed consent date and not performed per standard of care but on study purpose)
- Eligibility criteria deviation (any inclusion criteria not met or exclusion criteria met)
- Prohibited medication deviation (e.g., patients received other anticancer agents, investigational agents, or radiotherapy while on study treatment)
- Procedures/Tests deviation (ECG or ophthalmologic assessment or WHO performance status not performed at screening visit)
- Investigational product administration deviation (Overdose; Screening assessment date not within 28 days before start of treatment; Incorrect procedure for T790M obtainment; New or worsening pulmonary symptoms or radiological abnormality suggestive of Interstitial Lung Disease (ILD) observed, but study treatment not interrupted; Patient experiencing grade 3 QT interval corrected per Fredericia's formula (QTcF) with QTcF prolongation, but study treatment not interrupted)
- Withdrawal criteria deviation (Any withdrawal criteria met)
- Adverse Event (AE) / Serious Adverse Event (SAE) deviation (SAE / AE of special interest not reported in CRF within 24 hours of become aware)

The categorization of these as major deviations is not automatic and will depend on the duration and the perceived effect on efficacy.

All protocol deviations are defined in Protocol Deviation Specification document version 5.0 where a category Programmable / Observable is assigned to each deviation. Programmable deviations are programmed while Observable are checked manually during monitoring visits. Programmable deviations are then imported, and observable deviations are entered in a Protocol Deviation Tool according to classification defined in the Protocol Deviation

Specification. All deviations are then reviewed and classified on a monthly basis as Major/Minor.

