### 3.1.4 Response Rate (RR)

Response Rate is defined as the number (%) of patients with a best response (according to investigator assessment as recorded in the tumour evaluation CRF) of ‘responding’, regardless of the method of evaluation, and will be based on a subset of the FAS consisting of patients with at least one documented response assessment. Data obtained up until progression, or last evaluable assessment in the absence of progression, will be included in the assessment of response rate. Patients who discontinue treatment without progression, receive a subsequent anti-cancer therapy and then respond will not be included as responders in the RR.

In addition, a sensitivity analysis of RR will be performed including patients who died prior to any response assessment and classifying them as non-responders.

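### The documents disagree on whether cytotoxic drugs may be taken with AZD9291; separately, the response-rate rule does not cover concurrent anti-cancer therapy

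*Protocol*

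**What the plan says.** On co-administration:

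- Protocol Appendix B, Table 7 gives one piece of advice for rosuvastatin, sulfasalazine, doxorubicin, daunorubicin and topotecan: "Drugs are permitted but caution should be exercised and patients monitored closely for possible drug interactions". The heading above it reads "Medicines whose exposures may be affected by azd9291 that AstraZeneca considers may be allowed with caution".
- Protocol 4.1 says "Concomitant treatments, other than anti-cancer treatments, should be taken according to local medical practice", and the next sentence adds "There are no restrictions on concomitant use in this study except per exclusion criteria". It then advises avoiding products known to interact with AZD9291 and refers to Appendix B.
- Protocol 4.3 opens with "Patients may be discontinued from AZD9291 treatment in the following situations" and includes in its list "Patient starts receiving additional anti-cancer therapy".
- SAP 2.2 has the category "Prohibited medication deviation (e.g., patients received other anticancer agents, investigational agents, or radiotherapy while on study treatment" under its major deviations. It adds that the major label is not automatic and depends on duration and perceived effect on efficacy.
- SAP Appendix 2 includes doxorubicin among the chemotherapies.

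On response, SAP 3.1.4 uses data up to progression, or up to the last evaluable assessment if there is no progression. Its only exclusion for other therapy is: "Patients who discontinue treatment without progression, receive a subsequent anti-cancer therapy and then respond will not be included as responders in the RR".

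**The concern.** There are two separate problems.

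The first is the instruction to sites. Table 7 expressly concerns use together with AZD9291, and it permits a drug that the SAP counts as chemotherapy. SAP 2.2 calls the same use prohibited. A site that follows Table 7 can therefore generate a record that the deviation review classes as a breach. The objective in both documents is the efficacy and safety of AZD9291 as a single agent, so the documents should give one answer.

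The second is the response-rate derivation. SAP 3.1.4 clearly means to keep responses to other therapy out of the numerator, but its condition starts with stopping AZD9291. A patient who stays on AZD9291, adds another anti-cancer agent before progression and then has a first response falls outside that condition and is counted as a responder to single-agent treatment.

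**Working it through.** **Step 1. Compare the passages on co-administration.**

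| Source | Position on an anti-cancer agent taken with AZD9291 | Force |
|---|---|---|
| Protocol Appendix B, Table 7 | Permitted with caution for the named drugs | Explicit permission |
| Protocol 4.1, first sentence on concomitant treatment | Outside what local practice may decide | Carve-out, no explicit ban |
| Protocol 4.1, next sentence | No restriction beyond the exclusion criteria | Permissive; no exclusion criterion in 3.2 bars concurrent chemotherapy |
| Protocol 4.1, interaction advice | Products known to interact should be avoided | Advisory |
| Protocol 4.3 | A situation in which AZD9291 may be discontinued | Discretionary |
| SAP 2.2 | Prohibited-medication deviation | Named category; major status decided case by case |

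Permitted in Table 7 and prohibited in SAP 2.2 cannot both hold for doxorubicin. That conflict needs no outside knowledge, because the SAP itself lists the drug as chemotherapy. Daunorubicin and topotecan are not on that list; the conflict does not depend on them. The lead-in to Table 9 in the same appendix makes its permission subject to other exclusions and restrictions. Table 7 has no such proviso.

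**Step 2. Trace a patient through SAP 3.1.4.** Suppose a patient on AZD9291 starts another anti-cancer agent, continues AZD9291 and has a first recorded response before progression.

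- The patient is in the FAS, since one dose is enough (SAP 2.1).
- The response lies inside the data window, which closes at progression and not at the start of other therapy.
- The exclusion does not apply, because AZD9291 was not discontinued.
- Result: responder.

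This follows from SAP 3.1.4 alone and would be the same if Table 7 did not exist. Patients who had already responded before the other agent started, and those who add an agent only at or after progression, are unaffected.

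**Step 3. Size the effect on the response rate.** The documents give no planned response-rate precision to reproduce and no expected number of such patients, so this is an illustration.

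Inputs: N = 3500 (protocol synopsis). Response rate 60%, assumed as the middle of the 50% to 70% that protocol 1.4.2 reports for T790M-positive patients in an earlier study. Responders = 0.60 × 3500 = 2100.

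- Normal approximation: half-width = 1.96 × √(0.6 × 0.4 / 3500) = 1.6 points.
- Clopper-Pearson, the SAP's method: 58.35% to 61.63%, half-width 1.64 points. At 50% the half-width is 1.67 and at 70% it is 1.53.

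Let k be the number of patients whose first response came after another agent was started. If they become non-responders, the rate is (2100 − k)/3500.

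| Assumed share of 3500 | k | Response rate | Fall (points) |
|---|---|---|---|
| 0.1% | 4 | 2096/3500 = 59.89% | 0.1 |
| 0.5% | 18 | 2082/3500 = 59.49% | 0.5 |
| 1% | 35 | 2065/3500 = 59.00% | 1.0 |
| 2% | 70 | 2030/3500 = 58.00% | 2.0 |

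The rate would reach its own lower confidence limit at k = 2100 − 0.5835 × 3500 = 57.75, that is 58 patients or about 1.7% of 3500. The actual denominator is patients with at least one response assessment, so it will be somewhat below 3500 and the interval slightly wider.

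**Step 4. Check the other endpoints.** OS counts death from any cause in all dosed patients. PFS is defined in protocol 9.2 and SAP 3.1.2 alike as running regardless of other anti-cancer therapy. Neither derivation depends on the exclusion in SAP 3.1.4.

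**The case against.** The strongest reply is that Table 7 is generic interaction guidance. Its lead-in concerns sensitive BCRP substrates, and it supports section 4.2, which is about monitoring patients who take such medication. With the carve-out and the avoidance advice in 4.1, the protocol as a whole points away from adding chemotherapy. That is a fair reading of the likely intent. It does not remove the conflict, because Table 7 says the opposite without a proviso and 4.1 itself goes on to disclaim restrictions beyond the exclusion criteria.

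Other parts of the reply stand in full, and they rule out stronger readings:

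- A reader might infer that following Table 7 makes the patient a major deviator. SAP 2.2 says that label is not automatic.
- A reader might infer that 4.3 requires AZD9291 to be stopped. Its wording is discretionary.
- A reader might infer that Table 7 causes combination-treated patients to be counted as single-agent responders. The cause is SAP 3.1.4, which would do the same for any concurrent agent.
- A reader might extend the criticism to PFS. Ignoring other therapy there is a stated choice, consistent across both documents.

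It is also true that SAP 2.2 provides for a review of major deviations before database lock, with possible sensitivity analyses. These are optional and do not alter the RR definition.

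**Conclusion.** Two limited points hold. The documents give sites and the deviation review conflicting instructions on cytotoxic drugs taken with AZD9291, shown beyond dispute for doxorubicin. Independently, the response-rate rule excludes responses after subsequent therapy but counts first responses on concurrent therapy as responses to single-agent treatment.

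The numerical effect is probably very small. It is at most 1 point of response rate per 1% of patients affected, and reaches that only if every affected patient responded and did so first after the other agent began. The comparison with a half-width of about 1.6 points assumes a 60% rate and N = 3500. The documents give no frequency, so the shares above are assumptions and not estimates. The documents do not support a claim of material bias in the study's efficacy results: OS, the primary efficacy outcome, and PFS are derived as before. The case for acting rests on the contradictory instruction and on completing a rule that SAP 3.1.4 already half states.

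**What to change.** 1. Reconcile Appendix B Table 7 with protocol 4.1 and 4.3 and SAP 2.2, so that one rule governs anti-cancer agents taken with AZD9291. Which rule applies is for the sponsor to decide.
2. In SAP 3.1.4, extend the exclusion to responses first recorded after the start of any non-study anti-cancer therapy, concurrent or subsequent. Handle these patients as the existing rule does: they are not counted as responders. State whether radiotherapy is included, since SAP 2.2 puts it in the same deviation category.
3. Confirm that the CRF captures start dates of such therapy for all patients. This cannot be taken for granted. Protocol Table 4 marks concomitant medication at visits but mentions no dates, section 5 ties its collection to SAEs, events of special interest and events leading to dose modification, and Appendix B asks for wider recording. The SAP's imputation rules for partial concomitant-medication dates show that dates are expected where a medication is recorded, but not that recording is complete.

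The cost is an edit to the appendix, one added condition in the derivation and a check of the CRF. If start dates are not captured for everyone, data collection would have to be extended as well. The reported response rate may be marginally lower.

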### Drugs that may prolong qt interval

The drugs listed in this section are taken from information provided by The Arizona Center for Education and Research on Therapeutics and The Critical Path Institute, Tucson, Arizona and Rockville, Maryland. Ref: <http://www.arizonacert.org/medical-pros/drug-lists/drug-lists.htm>.

### Drugs known to prolong QT interval

The following drugs are known to prolong QT interval or induce Torsades de Pointes and should not be combined with AZD9291. Recommended withdrawal periods following cessation of treatment with these agents are provided in the table.

**Table 8 Drugs prolonging QT interval**

Contraindicated drug	Withdrawal period prior to AZD9291 start
Clarithromycin, droperidol, erythromycin, procainamide	2 days
Cisapride, disopyramide, dofetilide, domperidone, ibutilide, quinidine, sotalol, sparfloxacin, thioridazine	7 days
Bepidil, chlorpromazine, halofantrine, haloperidol, mesoridazine	14 days
Levomethadyl, methadone, pimozone	4 weeks
Arsenic trioxide	6 weeks*
Pentamidine	8 weeks
Amiodarone, chloroquine	1 year

\* Estimated value as pharmacokinetics of arsenic trioxide has not been studied

### Drugs that may possibly prolong QT interval

The use of the following drugs is permitted (notwithstanding other exclusions and restrictions) provided the patient has been stable on therapy for the periods indicated.

**Table 9 Drugs that may prolong QT interval**

Drug	Minimum treatment period on medication prior to AZD9291 start
Alfuzosin, chloral hydrate, ciprofloxacin, dolasetron, fosfarnet, galantamine, gemifloxacin, isradipine, ketoconazole, levofloxacin, mexiletine, nifedipine, octreotide, ofloxacin, ondansetron, quetiapine, ranolazine, telithromycin, tizanidine, vardenafil, venlafaxine, ziprasidone	2 days

**Table 9**      **Drugs that may prolong QT interval**

Drug	Minimum treatment period on medication prior to AZD9291 start
Amantadine, amitriptyline, amoxapine, clozapine, doxepin, felbamate, flecainide, fluconazole, fosphenytoin, gatifloxacin, granisetron, imipramine, indapamide, lithium, moexipril/HCTZ, moxifloxacin, risperidone, roxithromycin, sertraline, trimethoprim-sulfa, trimipramine, voriconazole	7 days
Azithromycin, citalopram, clomipramine, itraconazole, nortriptyline, paroxetine, solifenacin, tacrolimus	14 days
Fluoxetine	5 weeks
Protriptyline	6 weeks
Tamoxifen	8 weeks

## **Appendix C    Actions Required in Cases of Combined Increase of Aminotransferase and Total Bilirubin - Hy's Law**

### **Introduction**

During the course of the study the Investigator will remain vigilant for increases in liver biochemistry. The investigator is responsible for determining whether a patient meets potential Hy's Law (PHL) criteria at any point during the study.

The Investigator participates, together with AstraZeneca clinical project representatives, in review and assessment of cases meeting PHL criteria to agree whether Hy's Law (HL) criteria are met. HL criteria are met if there is no alternative explanation for the elevations in liver biochemistry other than Drug Induced Liver Injury (DILI) caused by the Investigational Medicinal Product (IMP).

The Investigator is responsible for recording data pertaining to PHL/HL cases and for reporting Adverse Events (AE) and Serious Adverse Events (SAE) according to the outcome of the review and assessment in line with standard safety reporting processes.

### **Definitions**

#### **Potential Hy's Law (PHL)**

A Potential Hy's Law (PHL) case is defined as a study subject with an increase in serum Aspartate Aminotransferase (AST) or Alanine Aminotransferase (ALT)  $\geq 3x$  Upper Limit of Normal (ULN) together with Total Bilirubin (TBL)  $\geq 2x$ ULN irrespective of serum Alkaline Phosphatase (ALP), at any point during the study following the start of study medication.

#### **Hy's Law (HL)**

A Hy's Law (HL) case is defined as a study subject with an increase in serum AST or ALT  $\geq 3x$  ULN together with TBL  $\geq 2x$ ULN, where no other reason can be found to explain the combination of increases, eg, elevated serum ALP indicating cholestasis, viral hepatitis, another drug.

For PHL and HL to be met the elevation in transaminases must precede or be coincident with (ie, on the same day) the elevation in TBL, but there is no specified timeframe within which the elevations in transaminases and TBL must occur.

#### **Identification of potential Hy's law cases**

In order to identify cases of PHL it is important to perform a comprehensive review of laboratory data for any patient who meets any of the following identification criteria in isolation or in combination:

- ALT  $\geq 3x$ ULN
- AST  $\geq 3x$ ULN
- TBL  $\geq 2x$ ULN.

The Investigator will without delay review each new laboratory report and if the identification criteria are met will:

- Determine whether the patient meets PHL criteria (see definition within this Appendix for definition) by reviewing laboratory reports from all previous visits

#### **Follow-up**

##### **Potential Hy's Law Criteria not met**

If the patient does not meet PHL criteria the Investigator will:

- Perform follow-up on subsequent laboratory results according to the guidance provided in the Clinical Study Protocol.

##### **Potential Hy's Law Criteria met**

If the patient does meet PHL criteria the Investigator will:

- Determine whether PHL criteria were met at any study visit prior to starting study treatment in the presence of liver metastases
- Notify the AstraZeneca representative who will then inform the central Study Team

The Study Physician contacts the Investigator, to provide guidance, discuss and agree an approach for the study patients' follow-up and the continuous review of data. Subsequent to this contact the Investigator will:

- Monitor the patient until liver biochemistry parameters and appropriate clinical symptoms and signs return to normal or baseline levels, or as long as medically indicated
- Investigate the etiology of the event and perform diagnostic investigations as discussed with the Study Physician
- If at any time (in consultation with the Study Physician) the PHL case meets serious criteria, report it as an SAE using standard reporting procedures

#### **Review and Assessment of potential Hy's law cases**

The instructions in this Section should be followed for all cases where PHL criteria are met.

No later than 3 weeks after the biochemistry abnormality was initially detected, the Study Physician contacts the Investigator in order to review available data and agree on whether there is an alternative explanation for meeting PHL criteria other than DILI caused by the IMP. The AstraZeneca Medical Science Director and Global Safety Physician will also be involved in this review together with other subject matter experts as appropriate.

According to the outcome of the review and assessment, the Investigator will follow the instructions below.

If there **is** an agreed alternative explanation for the ALT or AST and TBL elevations, a determination of whether the alternative explanation is an AE will be made and subsequently whether the AE meets the criteria for a SAE:

- If the alternative explanation is **not** an AE, record the alternative explanation on the appropriate CRF
- If the alternative explanation is an AE/SAE, record the AE /SAE in the CRF accordingly and follow the AZ standard processes

If it is agreed that there is **no** explanation that would explain the ALT or AST and TBL elevations other than the IMP:

- Report an SAE (report term ‘Hy’s Law’) according to AstraZeneca standard processes.
  - The ‘Medically Important’ serious criterion should be used if no other serious criteria apply
  - As there is no alternative explanation for the HL case, a causality assessment of ‘related’ should be assigned.

If, there is an unavoidable delay, of over 3 weeks, in obtaining the information necessary to assess whether or not the case meets the criteria for HL, then it is assumed that there is no alternative explanation until such time as an informed decision can be made:

- Report an SAE (report term ‘Potential Hy’s Law’) applying serious criteria and causality assessment as per above
- Continue follow-up and review according to agreed plan. Once the necessary supplementary information is obtained, repeat the review and assessment to determine whether HL criteria are met. Update the SAE report according to the outcome of the review.

